2 INTRODUCTION: BACKGROUND AND RATIONALE

This study will be conducted in compliance with the protocol, International Conference on Harmonization (ICH), Good Clinical Practice (GCP) guidelines and applicable regulatory requirements.

2.1 Background Information

A punctal plug, also known as tear duct plug or lacrimal plug, is a small medical device that is inserted into the nasolacrimal duct (puncta) of an eye to block (occlude) the drainage of tear fluid. Over the years several models of punctal plugs have been approved and are commercially available. Punctal plugs are classified by the FDA as a Class II Pre-Amendment medical device. Furthermore, plugs are not identified as significant risk devices on the FDA Information Sheet titled “Significant Risk and Non-Significant Risk Medical Device Studies.”

Occlusion of the puncta with punctal plugs has been a treatment for lacrimal deficiency in patients with dry eye for over the last 30 years ([Freeman 1975](#)). Since then, punctal plugs have been used extensively in primary eye care and are considered safe and effective in the treatment of dry eye ([Freeman 1975](#); [Willis et al. 1987](#); [Tuberville et al. 1982](#); [Fayet et al. 1990](#)). Since the inception of punctal plugs, several materials and designs have been developed with a host of products available on the market. While the designs have slight differences in architecture, the basic mechanism of action in treating dry eye with punctal plugs is basically the same, the conservation of naturally produced tears by physical occlusion of the lacrimal punctum.

Although Mati’s punctal plug designs are novel, the types of materials and techniques for insertion of the plugs are the same as other commercially marketed punctal plugs. Therefore Mati punctal plugs do not represent any more risk to human subjects than the risk associated with currently marketed punctal plugs however; the unique design of Mati punctal plug has shown a significant improvement in plug retention when compared to other marketed plugs.

2.2 Rationale

To evaluate the effect of Mati’s non-significant risk, non-drug eluting (NDE) L68 StableFit® punctal plug on the tear lake. In addition, evaluate the insertion/removal characteristics and subjects’ acceptance of Mati’s NDE L68 StableFit® punctal plugs.

2.3 Potential Risks and Benefits

The risks of the NDE L68 StableFit® punctal plug is not fully known but are expected to be similar to those observed for commercial punctal plugs, which are considered to be low. Some risks associated with punctal plug use are discomfort, epiphora, loss of plug, inflammation, and subconjunctival hemorrhage. Less common, but serious, side effects are pyogenic granuloma, damage to the muscle at the opening of the punctum, canaliculitis, or migration of the plug into the canalicula, requiring irrigation or surgery. In controlled clinical trials of the Mati punctal plugs, rates of serious adverse device events have been less than 1 percent ([Fayet 1990](#), [Balaram 2001](#), [Kim 2005](#)).

There are no treatment benefits to study participants. Study subjects will receive regular eye exams.

3 OBJECTIVES AND PURPOSE

To evaluate the effect of the NDE L68 StableFit® punctal plug on the tear lake. In addition, evaluate the insertion/removal characteristics and assess the subjects' acceptance of the NDE L68 StableFit® punctal plug.

4 STUDY DESIGN AND ENDPOINTS

4.1 Description of the Study Design

This is a Non-Significant Risk (NSR) medical device, multi-center, open-label clinical study. Each study subject that qualifies at the baseline visit will receive an NDE L68 StableFit® punctal plug in the lower punctum in one of their eyes. All study plugs will remain in the study subject's lower punctum for a period of 28 + 4 days after insertion.

4.2 Study Endpoints

The study will be complete when up to 40 study subjects (40 eyes) have been evaluated at Visit 3 (28 + 4 days post-insertion) or have been terminated from the study.

4.2.1 Primary Study Endpoint

The primary study endpoint will be the comparison of the tear lake volume at baseline with the tear lake volume at each follow-up visit.

4.2.2 Secondary Study Endpoints

Secondary study endpoints will evaluate the investigator's evaluation of epiphora, insertion/removal characteristics of the NDE L68 StableFit® punctal plug, and Investigators' evaluation of the study subjects' acceptance of the NDE L68 StableFit® punctal plug.

4.2.3 Safety Endpoints

Safety assessments will include any clinically significant slit-lamp biomicroscopy findings, any extrusions of a punctal plug, and incidence and severity of any reported ADEs after punctal plug insertion.

5 STUDY ENROLLMENT AND WITHDRAWAL

5.1 Study Population

Up to 40 normal healthy volunteers who meet all study inclusion/exclusion criteria will be enrolled in to the study. A subject will be allowed to use ocular drops during the study however, the subject must discontinue the use of all drops at least one hour prior to a study examination.

5.2 Study Subject Inclusion Criteria

The following are inclusion criteria for potential study subjects' wishing to participate in this study:

- a. A male or female subject, 18 years of age or older, in good general health at the time of the baseline examination, who may or may not have a mild to moderate dry eye condition
- b. A subject must be able to read, comprehend and be willing to give HIPAA authorization and informed consent
- c. A subject must be willing to have a punctal plug inserted in the lower punctum of one of their eyes
- d. Subject must be willing to comply with all study instructions, agree to make all office appointments, and complete the entire course of the study.

5.3 Study Subject Exclusion Criteria

The following are exclusion criteria for potential study subjects' wishing to participate in this study:

- a. A subject with a history of complications, adverse events, trauma or disease in the nasolacrimal area, whether or not it was due to punctal plug wear, including but not limited to dacryocystitis, inflammation or canaliculitis in either eye
- b. A subject with a history of intolerance to punctal plugs
- c. A subject with structural lid abnormalities (e.g., ectropion, entropion) in either eye
- d. A subject with any clinically significant lid, conjunctival or corneal findings in either eye at the baseline visit
- e. A subject with a puncta >0.9 mm prior to dilation in either eye
- f. A subject with a severe dry eye condition
- g. A subject experiencing epiphora in either eye
- h. A subject experiencing any clinically significant ocular pain or discomfort in or around either eye at the baseline visit
- i. A subject with a known sensitivity to any inactive ingredient of the punctal plug, silicone, topical anesthetic, or any other products required for the study
- j. A subject currently participating or has participated in another clinical trial within 30 days prior to enrollment.

5.4 Strategies for Recruitment and Retention

To increase study subject enrollment and retention in the study, sites should dedicate an individual [Clinical Research Coordinator (CRC)] who is well informed regarding the study design, study specific inclusion/exclusion criteria and visit schedule as the main contact who is readily available to answer all potential subject questions and/or concerns about participating in the clinical study.

The CRC should be prepared to discuss with a potential study subject the differences in the amount of time, examination procedures and visit schedule they would experience if they agreed to participate in the study. In addition, should a subject agree to participate in the study, the CRC would be readily available as his/her main contact person while participating in the study.

To encourage recruitment and retention of a study subject, sites should offer a subject reimbursement for transportation cost and a stipend for his/her time and effort for participation, offer less waiting time in the doctor's office by scheduling more flexible and reliable appointment times.

5.5 Study Subject Withdrawal or Termination Criteria

After insertion of a study plug, the Investigator may withdraw a study subject from the study if in their medical judgment it is in the study subject's best interest.

Each study subject will be informed that they are free to withdraw from the study at any time. If a study subject is prematurely withdrawn from the study, the reason(s) for withdrawal must be recorded on the relevant page of the subject's case report form (CRF). Study subjects who withdraw from the study will be replaced.

The Investigator, the Investigator in consultation with the Medical Monitor, or the Medical Monitor may exercise his or her medical judgment to terminate a study subject's participation in the study if it is in the best interest of the study subject. A terminated study subject will be followed through Visit 3 (28 days after insertion of the punctal plug) or until the condition has resolved or has become medically stable.

Medical Monitoring for this study will be conducted by:

[name]

Phone (Office): [contact]

Phone (Cell): [contact]

Email: [contact]

The name of the Medical Monitor and contact information will be provided to each study site.

Mati Therapeutics Inc. reserves the right to terminate the study at any time. Every effort will be made to collect all data required by the protocol during or following the termination of a study subject.

5.5.1 Reasons for Termination, Discontinuation or Disqualified

At a study subject last visit (scheduled or unscheduled), they will have their punctal plug removed and a study exit case report form (CRF) must be completed, whether or not the study subject completed the final study visit (Visit 3, 28 days after plug insertion). The reason for any early exit from the study will be indicated on the study exit form and all efforts will be made to complete and report the observations as thoroughly as possible. The primary reason for a study subject's early exit from the study should be selected from the following standard categories.

5.5.1.1 Termination from the study

A study subject will be terminated from the study if in the Investigator's medical judgment, it was in the best interest of the study subject that developed or reported: a) a clinically significant ocular sign(s) or symptom(s) b) reported serious ADE, regardless of relation to the study device or has died or c) extrusion of a punctal plug.

A terminated study subject will return to the clinic for an end of study safety evaluation and the removal of the punctal plug. A terminated study subject will receive appropriate treatment at the discretion of the Investigator. Notification of termination will be clearly documented on the appropriate Case Report Form. A terminated study subject is considered to have completed the study and will NOT be replaced.

5.5.1.2 Discontinued from the study

A study subject will be discontinued from the study if the Investigator is unable to insert the study punctal plug in to either eye of the study subject's lower punctum, has personal reasons, or has a desire to withdraw from further participation in the study in the absence of a medical need as determined by the Investigator. Other reason – if the study subject was discontinued for a reason other than those listed above, the Investigator must specify the reason.

A study subject may voluntarily discontinue (withdraw) from the study at any time they choose. Notification of discontinuation will be clearly documented on the appropriate Case Report Form. If a study subject elects to withdraw from the study during the study follow-up period, the Investigator must make every effort to have the study subject return to the clinic for an end of study safety evaluation and the removal of their punctal plug. A study subject who is discontinued from the study will be replaced.

5.5.1.3 Disqualification from the study

A study subject will be disqualified from the study if there was a failure to obtain written informed consent or HIPAA Authorization, improper entry (did not meet all inclusion/exclusion criteria).

Notification of disqualification will be clearly documented on the appropriate Case Report Form. The Investigator must make every effort to have the study subject return to the clinic for an end of study safety evaluation and the removal of the punctal plug. A study subject disqualified from the study will be replaced.

5.6 Premature Termination or Suspension of Study or Study Site

Mati Therapeutics Inc. reserves the right to terminate or suspended the study at any time. Every effort will be made to collect all data required by the protocol during or following the study subject's early termination visit.

If representatives of Mati Therapeutics Inc., the Principal Investigator, the Study Monitor [Clinical Research Associate (CRA)], the Medical Monitor, or the FDA officials discover conditions arising during the study that indicate that the study will be halted or that participation by the study center will be terminated, this action may be taken after appropriate consultation with representatives of

Mati Therapeutics Inc., the Principal Investigator, the CRA, and the Medical Monitor. Conditions that may warrant termination of the study include, but are not limited to the following:

- a. The discovery of an unexpected, serious, or unacceptable risk to a study subject enrolled in the study
- b. A decision on the part of Mati Therapeutics Inc. to suspend or discontinue testing, evaluation, or development of the product
- c. Failure of the Principal Investigator to enroll study subjects into the study at an acceptable rate
- d. Failure of the Principal Investigator to comply with pertinent FDA regulations and ICH Guidelines
- e. Submission of knowingly false information from the research facility to Mati Therapeutics Inc., or designee, the CRA, the Medical Monitor, or the FDA
- f. Insufficient adherence to protocol requirements.

[figure not shown]
Study termination and follow-up will be performed in compliance with the conditions set forth in 21 CFR 812.40 and 21 CFR 812.43.

6 STUDY DEVICE

6.1 Mati's Non-Significant Risk, Non-Drug Eluting (NDE) L68 StableFit® punctal plug

The NDE L68 StableFit® punctal plug consists of inactive medical grade silicone and 2% green colorant. The NDE L68 StableFit® punctal plug design is shown in Figure 1. The NDE L68 StableFit® punctal plug is provided pre-loaded on an insertion tool, packaged in a preformed rigid tray with a foil laminate lid heat sealed onto the tray and sterilized.

Figure 1: Proprietary NDE L68 StableFit® Punctal Plug Design

6.2 Procedure for Insertion of the NDE L68 StableFit® Punctal Plug

The procedure for inserting a Mati's NDE L68 StableFit® punctal plug is similar to those for commercial plugs. In preparation for the insertion of the NDE L68 StableFit® punctal plug, the subject may be seated at the slit lamp, or placed in a reclined position:

- a. To anesthetize the area around the lower punctum, place a drop of topical anesthetic such as proparacaine or lidocaine on the eye. Then use a proparacaine or lidocaine soaked cotton-tipped swab. Place the swab directly on the lower punctum of the eye to be inserted for ~30 to 60 seconds (proparacaine or lidocaine can be irrigated into the canaliculus for better anesthesia if desired)
- b. Using the Coroneo punctal dilator, the dilator is engaged vertically (straight down) in the punctum with a gentle twisting motion. The dilator is then quickly moved 90 degrees parallel to the lid margin passing it into the proximal canaliculus dilating the punctum
- c. The punctum must be dilated to at least 1.0 mm. Once the punctum is dilated to 1.0 mm, leave dilator in place for 15 to 30 seconds to allow the sphincter to fully relax. It is very important to fully dilate the punctum to 1.0 mm.

While dilating, prep the study punctal plug to be inserted in the lower punctum of the study subject's eye.

NOTE: For small puncta, hold and rotate the dilator in the punctum and canaliculus for as long as required to achieve dilation to 1.0 mm. This may take some considerable time. Dilation may require very firm pressure. Add more anesthesia if needed.

- d. Remove dilator and immediately attempt to insert the plug before the sphincter starts to close
- e. Position the plug end of the insertion instrument over the study subject's punctum
- f. Gently insert the plug, coming straight down perpendicular to the punctum until the cap of the plug is flush with the lid margin
- g. Once the plug is in the proper position, press the release button and pull the insertion instrument away from the study subject's punctum
- h. After insertion, the punctal opening should be visually inspected using a slit-lamp to confirm the retention and proper placement of the study punctal plug, with the cap still visible. The position of the study punctal plug may be adjusted with forceps, if necessary.

NOTE: The punctum may constrict before the plug can be inserted, additional dilation would then be required. If a plug is partially inserted (e.g., cap not flush with the lid margin) the plug should be removed and the punctum re-dilated or dilated to a larger diameter. Placement of the plug can then be re-attempted. Multiple attempts are sometimes necessary however; lubricants are not to be used.

Any questions or concerns regarding the insertion or removal of a punctal plug contact:

[name]
Phone (Office): [contact]
Phone (Cell): [contact]
Email: [contact]

6.3 Instruction for Study Subjects

Instruct each study subject not to attempt to remove or adjust the punctal plug on his/her own. If a punctal plug is extruded and the subject can recover it, the plug must be returned to the study center. In addition, encourage each study subject to restrict eye rubbing and be mindful of his/her study eye when swimming or in other activities.

6.4 Procedure for Removal of Punctal a Plug

The punctal plug can be removed from the study subject's punctum using ophthalmic forceps and a gentle tugging motion. A drop of anesthetic may be administered if necessary.

- a. Stabilize/constrain eyelid with fingers or with help from assistant
- b. It is recommended that a 0.12 1x2 teeth Castroviejo Suture forceps or similar toothed forceps with platforms should be used for plug removal.

NOTE: Using a jeweler's forceps is not advisable

- c. Teeth should be placed on the far side of the plug with the blades straddling the neck of the plug just under the cap
- d. Care must be taken not to grasp the outermost edge of the cap on the punctal plug as this may cause the cap to tear and separate, making it difficult to remove the plug from the canaliculus and/or causing plug intrusion
- e. The teeth should not be used to grasp the plug but are used instead to prevent the blades of the forceps from sliding off the neck. Grasping the plug with the teeth may fracture it
- f. The motion to remove should be towards the medial canthus (not up or temporally), which is necessary to disengage the heel of the plug.

If the cap becomes separated, try to remove the plug using toothed 0.12 forceps (0.12 Castroviejo forceps or similar) by grasping the neck of the plug through the punctum. If this is not possible, and it doesn't seem as if the plug will lodge in the canal, and only if you feel comfortable doing so, you may attempt to irrigate the canal until the plug flushes out of the nasolacrimal duct.

NOTE: Please exercise clinical judgment when proceeding. Referral to tertiary care is advised in cases where the plug cannot be retrieved by massaging/milking through the punctal opening or by irrigation. Plug migrations are to be reported as an ADE however, a superficial migration, in which the plug is temporarily displaced, is visible with the slit lamp and can be easily repositioned, is not considered an ADE.

Removal of the study punctal plug immediately after insertion may result in the cap of the plug being torn off; if possible the Investigator should wait 30 to 60 minutes after insertion before attempting to remove a study punctal plug. However, if the plug tears or separates, report this as a technical complaint. Retain the plug for accountability of investigational supplies.

6.5 Punctal Plug – Unable to Insert / Extruded

6.5.1 Unable to Insert a Punctal Plug in Either Punctum

If a punctal plug cannot be inserted in to each eye after dilation, the study subject will be discontinued from the study and replaced.

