7.3 Study Visit Schedule

7.3.1 Visit 1: Day 0 - Screening (Prior to punctal plug insertion)

A potential study subject qualifications will be assessed according to the inclusion/exclusion criteria listed in the protocol (see Sections 5.2 and 5.3). Prior to undergoing any study-specific procedures, both the study Informed Consent and Authorization for Use/Disclosure of Health Information forms (HIPAA authorization) must be signed by a potential subject who has agreed to participate in the study. During this visit, the following information will be collected/evaluated and recorded in the appropriate sections of the study case report forms of a subject, prior to the sizing and dilation of the lower punctum for the planned study eye.

- a. Obtain informed consent and HIPAA authorization release
- b. Record the subject's demographic data and prior 7 days medical history
- c. Verify a subject has not used any ocular drops within the last hour prior to their baseline visit
- d. Record any subject reports of ocular signs or symptoms they are currently experiencing
- e. Slit-lamp examination of the planned study eye

7.3.2 Visit 1:Baseline - Day 0 (Insertion of a punctal plug - refer to Section 6.2 for details regarding the insertion of the NDE punctal plug)

After the screening examination, a qualified study subject will be sequentially assigned an ID number. In addition, the ID number and the study subject initials will be recorded on study case report forms, in lieu of recording his/her name, in order to maintain subject confidentiality.

Note: The investigator has the option of inserting the plug in either the left or right eye of the subject. However, if the investigator is unable to insert the plug in the first eye chosen, the investigator can insert the plug in the fellow eye as long as the fellow eye meets all study inclusion/exclusion criteria.

- f. Tear lake evaluation of the planned study eye prior to the sizing and dilation of the lower punctum
- g. Size evaluation of the punctum of the planned study eye prior to the dilation of the lower punctum
- h. After dilation, the study punctal plug is inserted in to the lower punctum of study eye, inspect the punctal plug using the slit-lamp, the position of a study punctal plug may be adjusted with forceps.
- i. Record any reported adverse device event(s)

j. After the study plug has been inserted in the lower puncta, the investigator will assess the insertion characteristics of the plug.

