10.4.3 Analysis of the Secondary Endpoint(s)

Secondary endpoints will be based on changes from baseline in the severity of epiphora. For the investigator's evaluation of the subject's acceptance of the punctal plug, data from all subjects will be evaluated. Investigator evaluation of insertion and removal characteristics will be tabulated by study subject and overall evaluation. For analyses using the intent-to-treat (ITT) data set, all data from all subjects with at least one assessment of epiphora, subject acceptability and punctal plug characteristics evaluations will be included. For the per protocol (PP) analyses dataset, data from subjects or visits with significant protocol deviations will be excluded.

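### The by-subject insertion ratings and the safety set cover only subjects with a plug successfully inserted, so failed attempts have no stated denominator

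*Combined protocol and SAP*

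**What the plan says.** Section 4.2.2 makes insertion and removal characteristics a secondary endpoint. The trigger for the per-subject insertion rating is in section 7.3.2, item j: "After the study plug has been inserted in the lower puncta, the investigator will assess the insertion characteristics of the plug". The synopsis (Visit 1, item k) and key E of the schedule of assessments agree.

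Two provisions deal with failure. The note in section 7.3.2 says that "if the investigator is unable to insert the plug in the first eye chosen, the investigator can insert the plug in the fellow eye", provided that eye qualifies. Section 5.5.1.2 says: "A study subject will be discontinued from the study if the Investigator is unable to insert the study punctal plug in to either eye", and section 6.5.1 adds replacement: "If a punctal plug cannot be inserted in to each eye after dilation, the study subject will be discontinued from the study and replaced". Neither asks for a rating of the eye that failed.

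For analysis, section 10.4.3 says: "Investigator evaluation of insertion and removal characteristics will be tabulated by study subject and overall evaluation". It names no success rate and no count of attempts. Section 10.4.4 makes subjects who were inserted with a plug evaluable for safety. It presents separately any adverse device event (ADE) between consent and exposure, but does not define exposure.

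Insertion is not a trivial step. Section 6.2 covers anesthesia, dilation and insertion, and warns that "Dilation may require very firm pressure". For a partly inserted plug, "the plug should be removed and the punctum re-dilated or dilated to a larger diameter", and "Multiple attempts are sometimes necessary".

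**The concern.** A table of insertion ratings is meant to tell the sponsor how the plug goes in. If the rating is made only when the plug has gone in, the hardest eyes are left out, and a reader cannot tell from the table how often insertion failed per eye or per subject. A first-eye failure rescued in the fellow eye appears simply as one rated, inserted subject.

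The safety set has the same condition. Anesthesia, dilation and attempted insertion come before success, so a subject who went through them without ending up with a plug has been exposed to the procedure but is not in the main denominator. Because the study describes a device and its insertion, this affects how two of its results can be reported. It does not affect the primary tear lake comparison in inserted eyes.

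**Working it through.** **1. Paths through the protocol text**

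| Path at Visit 1 | By-subject insertion rating required? | In the safety set (10.4.4)? |
|---|---|---|
| First eye inserted | Yes (7.3.2 j) | Yes |
| First eye fails, fellow eye inserted | For the inserted eye; none stated for the failed eye | Yes |
| Never inserted | None stated | No |

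**2. ADE start points**

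- Section 8.1: only events during insertion or later are recorded as ADEs.
- Section 8.5: events are documented starting at Visit 1.
- Section 10.4.4: treatment-emergent events are those after insertion; events before exposure are shown separately.

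An event during dilation in a never-inserted subject is documented under 8.5 and arguably falls within 8.1. It is not treatment-emergent under 10.4.4, and could be listed as pre-exposure only if exposure means a plug in place.

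**3. Illustrative size**

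The plan has no figure to reproduce: no failure rate is given and no sample size was calculated (10.5). The number 40 is the ceiling in section 4.2, taken here as the number inserted. All else is assumed:

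- q = first-eye failure rate: 5%, 10% or 20%
- a = share of first-eye failures followed by a fellow-eye attempt: 0.5 or 1
- c = chance that the fellow eye fails given that the first did: q (independent), 0.5, or 1 (complete dependence)

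P(inserted) = 1 − q + q·a·(1 − c), and subjects attempted N = 40 / P. First-eye failures = N·q; rescued = N·q·a·(1 − c); never inserted = N − 40.

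For q = 0.10, a = 1, c = 0.10: P = 0.99, N = 40.40, first-eye failures 4.04, rescued 3.64, never inserted 0.40. For q = 0.10, c = 1: P = 0.90, N = 44.44, first-eye failures 4.44, rescued 0, never inserted 4.44.

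| q | First-eye failures | Rescued | Never inserted | Never inserted, % of N |
|---|---|---|---|---|
| 5% | 2.0–2.1 | 0–1.9 | 0.1–2.1 | 0.3–5% |
| 10% | 4.0–4.4 | 0–3.6 | 0.4–4.4 | 1–10% |
| 20% | 8.3–10.0 | 0–6.7 | 1.7–10.0 | 4–20% |

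The failure rate mainly sets the first column. Between-eye dependence and fellow-eye use decide how failures split between rescued and never inserted.

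Eyes and subjects can give different pictures. In the independent 10% case, eyes attempted = 40.40 + 4.04 = 44.44. Success is then 40/44.44 = 90.0% of eyes but 40/40.40 = 99.0% of subjects.

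**4. Safety percentage**

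Suppose 2 of 40 inserted subjects have an ADE (2/40 = 5.0%) and 4 more were attempted but never inserted. Including them gives 2/44 = 4.5% if none had an ADE, 4/44 = 9.1% if two did, and 6/44 = 13.6% if all four did.

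**5. Linked wording on extrusion**

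In section 7.3.5, items b, c and e (acceptability, slit lamp, tear lake) end with a proviso about the plug not having been extruded. It can be read as limiting the assessment, or only its timing relative to removal. Section 6.5.2 terminates a subject who notices an extrusion; section 5.5.1.1 ties termination to the investigator's judgment; section 5.5 follows terminated subjects through Visit 3 or until resolved or stable. Separately, a subject who loses the plug before Visit 2 and has no later tear lake value can meet the ITT definition in section 10.1 (inserted, no major violation) but not the one in section 10.4.2 (at least one follow-up tear lake).

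**The case against.** The strongest reply is that failures are not lost. The discontinuation reason goes on the CRF (5.5.1.2), plugs are fully accounted for (6.6), and the end-of-study overall insertion assessment covers all enrolled subjects (note to 7.3.2). Performance complaints must be reported (8.6.2), and each investigator's summary counts discontinued subjects (11.5). The CRF is not in the documents and may record attempts. The endpoint is also insertion characteristics, not a success rate. This is fair, and it rules out any claim that failed insertions go unseen. But these records chiefly capture both-eye failures; none requires a rating or count of failed first eyes, and none gives the 10.4.3 table an attempted denominator.

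Three stronger readings are tempting and are not supported:

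- **That ADEs in a failed attempt are never recorded.** Section 8.1 includes events during insertion, and section 6.2 lists anesthesia and dilation as steps of the insertion procedure. Sections 8.2.1 and 8.5 also favor recording. What stands is the missing denominator and the inconsistent wording.
- **That the section 6.2 remarks on repeated attempts show unrated failures.** They describe re-attempts in the same punctum, and if these succeed the eye is rated. They show that difficulty is foreseen, no more.
- **That tear lake and acceptability are not collected after an extrusion.** The proviso in section 7.3.5 is ambiguous. Section 5.5 asks for every effort to collect required data, and section 5.5.1.1 for an end-of-study safety evaluation.

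It can also be said that the magnitudes are wholly assumed and span a wide range. That is so; they show what the structure allows and do not predict results.

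**Conclusion.** The point holds. On the protocol's own text, the by-subject insertion table is conditional on success, and the main safety denominator leaves out subjects who had dilation and attempted insertion but never received a plug. It rests on reading the rating trigger, the discontinue-and-replace rule and the safety set together, and on the CRF having no attempt item, which cannot be checked. The size is unknown because no failure rate is given, and no direction of bias can be claimed for the safety percentage. The undefined term exposure and the three ADE start points need reconciling whatever the failure rate. The extrusion wording and the two ITT definitions are secondary. The matter should be corrected because describing insertion is a stated objective, but it does not undermine the primary endpoint.

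**What to change.** 1. **Insertion.** Record the outcome and a rating for every eye attempted, successful or not. Report eyes inserted over eyes attempted and subjects inserted over subjects attempted, and list first-eye failures. If the CRF already captures this, cite it and add only the table.
2. **Safety set.** In section 10.4.4, define it as all qualified subjects in whom dilation for insertion, or plug insertion, was started, and show the inserted subset beside it. Sizing alone need not count: it is a screening step, since punctum size is an exclusion criterion (5.3 e). It does use anesthetic and the dilator, however, so the boundary should be stated explicitly.
3. **Terms.** Define exposure, and use one ADE start point in sections 8.1, 8.5 and 10.4.4.
4. **Secondary.** Reconcile sections 5.5, 5.5.1.1, 6.5.2 and 7.3.5 on what is collected after an extrusion. Label Visit 3 tear lake and acceptance results as plug-in-place where that applies. Use one ITT definition in sections 10.1 and 10.4.2.

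The cost is at most a small eye-level CRF item, one table and revised wording, with no added visits. The downside is that the insertion results may look less favorable than a success-only table, and the safety percentages may shift up or down.
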